2.3. Benefit/Risk Assessment

PF-06755347 is not expected to provide any clinical benefit to healthy participants but it may provide a transient increase in platelet count in participants with persistent or chronic ITP. This study is designed primarily to generate safety, tolerability, and pharmacokinetic data that will support further clinical development.

PF-06755347 has been shown to cause transient elevation in pro-inflammatory cytokines. Symptoms associated with CRS vary greatly and may be difficult to distinguish from other conditions. The more common symptoms include fever, nausea, headache, tachycardia, hypotension, rash and shortness of breath. The severity of symptoms can be mild to life threatening and thus there should be a high suspicion for CRS if these symptoms occur. Cytokines will be analyzed to determine if cytokine elevation consistent with CRS is observed (see [Section 10.10](#)). The severity of CRS will be assessed according to the most

recent consensus grading from the American Society for Transplantation and Cellular Therapy (ASTCT).²

For study participants with ITP, there is an increased risk of procedure-related bleeding/bruising from subcutaneous injections, mitigated by the lower bound of platelets in the eligibility criteria. An increased risk of thrombosis has also been reported in ITP.¹⁵ High dose single IV administration of PF-06755347 may transiently lower platelet counts in healthy participants, while repeat IV administration in non-clinical studies may also lower platelet counts. The predicted C_{max} with SC administration in ITP participants is approximately 6 fold lower than observed C_{max} at 1 mg/kg at which the reduction in platelet count was observed in healthy participant (see [Table 6](#)). More detailed information about the known and expected benefits and risks and reasonably expected adverse events of PF-06755347 may be found in the investigators brochure, which is the SRSD for this study.

Each study site should have a COVID-19 risk mitigation policy (RMP), which documents the site's COVID-19 virus testing strategy for participants and staff, social distancing measures, and management of COVID-19-like symptoms.

To account for the widespread deployment of COVID-19 vaccine during the COVID-19 pandemic, the benefit/risk analysis has assessed both the impact of PF-06755347 on risk of COVID-19 disease in study participants who may become infected with SARS-CoV-2 and the efficacy of COVID-19 vaccines.

The benefit/risk analysis for study participants for COVID-19 related illness during the COVID-19 pandemic is similar to the benefit/risk prior to COVID-19. PF-06755347 is proposed to be an immunomodulator similar to IVIg, and so its safety in humans can reasonably be predicted from clinical experience with IVIg. PF-06755347 is not an immunosuppressant that might render an individual more susceptible to the impact of COVID-19. IVIg has been used in COVID-19 infected individuals because of its known immunomodulatory effects and is reported in uncontrolled trials to be helpful in critically ill individuals. There are currently no reports of injury because of the immunomodulatory effects of IVIg in COVID-19 infected individuals.

In contrast, the benefit/risk analysis for study participants who are scheduled to receive or have received a COVID-19 vaccine suggests that appropriate interval between vaccination and administration of PF-06755347 is prudent because of the potential for an immunomodulatory effect to interfere with development of the intended immune response to the vaccine. While this has not been studied for PF-06755347, extrapolation from other immunomodulatory/immunosuppressive agents suggests at least a 28 day interval after completion of the vaccination course should be sufficient to allow a desired immune response.

By the time of discharge after study confinement on Day 8, approximately 3 terminal half-lives of the study drug will have elapsed. Coupled with the rapidity of the cytokine response to study drug, longer duration of confinement for additional observation appears unnecessary. The on-site follow up requirements for the study are standard timelines for participant safety.

3. OBJECTIVES AND ENDPOINTS

Primary Objective:	Primary Endpoints:

 To evaluate safety and tolerability following a single dose of PF-06755347 in the study population. 	
 Assessment of AEs, clinical laboratory tests, vital signs, body temperature, cardiac monitoring and cardiac telemetry (where collected) and 12-lead ECG.
Secondary Objective:	Secondary Endpoints:

 To characterize the plasma PK profile following a single of PF-06755347 in the study population. 	
 PK parameters derived from plasma PF-06755347 concentration:^a C_{max}, T_{max}, AUC_{last}, AUC_{inf}, $t_{1/2}$, if data permit.

 To evaluate the immunogenicity profile following a single dose of PF-06755347 in the study population. 	
 Incidence of the development of anti-drug antibody to PF-06755347.

 CCI [REDACTED] 	
 [REDACTED]
Tertiary Objective:	Tertiary Endpoints:

 To further characterize the plasma PK profile following a single dose of PF-06755347 in the study population. 	
 PK parameters derived from plasma PF-06755347 concentration:^a C_{max} (dn), AUC_{last} (dn), AUC_{inf} (dn), CL, V_{ss}, CL/F, and V_z/F, if applicable.

 CCI [REDACTED] 	
 Collection of biospecimens unless prohibited by local regulations or ethics committee decision. Additional information on collection and potential use is provided in the Biospecimens section.

a. For a complete definition of all PK parameters, refer to [Section 9.5.1](#).

4. STUDY DESIGN

4.1. Overall Design

This is a Phase 1, randomized, double-blind, Sponsor-open, placebo -controlled, first-in-human single -ascending dose study to evaluate the safety, tolerability, and PK of PF-06755347 in healthy adult male participants by IV and SC administration and in male or female participants with persistent or chronic ITP by SC administration. Personnel, trained in advanced cardiac life support, emergency resuscitative equipment and the management of anaphylaxis, are immediately available to treat systemic reactions under the supervision of a physician. IV fluids, epinephrine, antihistamine and methylprednisolone will be available for immediate parenteral use in the event of an anaphylactic reaction.

A schematic of the overall study design is provided in [Section 1.2](#) (note actual dose levels to be administered beyond the starting dose are subject to change, see [Section 4.2.1.3](#)). A total of approximately 75 healthy adult male participants are planned to be randomized to either receive PF-06755347 or placebo by intravenous or subcutaneous administration in a 3:1 allocation ratio. All participants with ITP will receive PF-06755347. Clinical data from the IV cohorts supporting the transition to SC dosing are summarized in the IB, Section 6. SC Cohorts 7-14 are planned, Cohort 7 will have 4 male participants (3 active and 1 placebo)

and Cohorts 9-11 will have 8 male participants (6 active and 2 placebo). Cohort 12 (optional Japanese cohort) will include approximately 4-8 male Japanese healthy participants and Cohorts 13 and 14 combined will include a maximum of 12 male or female participants with ITP. The total number of participants randomized will not exceed 87. The ITP cohort dosing will start after completion of the 50 mg dose cohort in HPs.

Participants within each cohort will be dosed using a sequential dosing scheme. For all cohorts, only a single participant will be dosed at any given time. Based on the emerging safety data to date with IV dosing, cytokine and laboratory abnormalities reach their peak levels within the first few hours following PF-06755347 C_{max} and are resolved within 24 hours. The C_{max} was predicted to be 24 -48 hours with SC administration, however preliminary data from Cohort 7 supports increasing the monitoring period to 96-hr for safety.

A safety review of the post-dose 72-hour data (96-hour for SC administration) will occur for every participant in order to proceed with dosing the next participant. A minimum of 96-hours (120-hours for SC administration) between dosing of consecutive participants. A safety review evaluation meeting may be required in order to proceed with dosing the next participant. The safety review period can be extended if deemed necessary at the discretion of any PI (in consultation with the Sponsor medical monitor). Dose levels selected for optional cohorts will be selected based on the assumption that resulting clinical exposures will not exceed protocol defined PK stopping limits.

Only males will be enrolled in the healthy participant cohorts in an attempt to reduce overall variability because there are significant gender variations in immune responses.¹⁶ Healthy Participants will be screened to ensure that they do not have any autoimmune disease or immune deficiency prior to enrollment. Participants with ITP that have active autoimmune disease in the opinion of the investigator will be excluded. Participants with a history of migraine will also be excluded so as not to confound pro-inflammatory adverse event assessments using the Common Terminology Criteria for Adverse Events (CTCAE) criteria. The age range will be 18-55 years in order to ensure adequate renal function and reduce the risk of thrombo-embolic events. Screening evaluation will occur within 56 days prior to dosing.

Male and female participants will be enrolled in the ITP cohorts. In adults, ITP is more common in females than in males. Therefore, it is important to allow for assessment of safety, tolerability and PK in both males and females.

PF-06755347 has been administered to male and female cynomolgus monkeys by IV infusion and SC bolus injection across a wide range of doses in multiple studies. PF-06755347 PK parameters (C_{max} , T_{max} , AUC_{168}) were similar between male and female cynomolgus monkeys at all doses. Additionally, incidence and magnitude of IL-6 or IL-1RA release was similar between the sexes. Therefore, nonclinical data support the expectation that no dose adjustment is needed in female participants in B7801001.

Eligible participants who meet the entry criteria will be admitted on Day -1 and are required to stay overnight through completion of Day 8 evaluations. At the discretion of the study site participants may be admitted on Day -2. Participants will return for outpatient visits per the Schedule of Activities (SoA) through approximately Day 36 (≤ 1 mg/kg IV dose level) or Day 71 (> 1 mg/kg IV dose level and all subcutaneous dose levels for a total of approximately 5 or 10 weeks study participation, respectively from first dose to final follow-up, excluding screening. The follow-up period may be extended for a participant and/or a cohort if any participant in the cohort tests positive for anti-drug antibody to PF-06755347 at the scheduled follow-up visit, or has detectable concentration of PF-06755347 at final follow-up visit.

If a participant discontinues during the study, the participant may be replaced at the discretion of the Sponsor in consultation with the PI. Doses in the dose escalation sequence may be repeated or adjusted depending on the results obtained during the study to explore different doses and/or infusion/dosing rates as needed. The total number of participants including the subcutaneous and optional cohorts will not exceed 87.

Some of the cohorts in the study may not be conducted if study objectives are deemed accomplished or if directed by emergent data. Participants in any cohort may be confined for a period beyond what is required in the SoA at the discretion of the investigator for safety reasons and/or to accommodate the frequency of required outpatient visits.

CCI

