Medication history	X	X ^c																										
Weight	X	X																							X		X	
Urine drug screening	X	X																										
FSH ^b	X																											
Serum Pregnancy ⁱ	X	X																										
Review contraception use	X	X																	X	X	X	X	X	X	X	X	X	
Physical examination ^d	X	X																	X	X	X	X	X	X	X	X	X	
Hematology & Coagulation (PT, INR, PTT, D-dimer & fibrinogen) Safety Labs	X	X										X	X		X	X		X	X	X	X	X	X	X	X	X	X	
Chemistry/Urinalysis/Other Safety Labs	X	X										X	X		X	X		X	X	X	X	X	X	X	X	X	X	

Table 3. Schedule of Activities for SC Cohorts of ITP Participants

Protocol Activity Abbreviations used in this table may be found in 10.14. Appendix 14: Abbreviations	Screen		Clinical Confinement																Outpatient Follow-Up Visits								
	-56 to -2	-1 ^a	1											2	3	4	5	6	8	11 ±2	15 ±2	22 ±2	29 ±2	36 ±3	50 ±3	71 ±3 or ET	
Hour(s) Post Dose			0 pre-dose	0.5	1	3	3.5	4	5	6	8	12	24	36	48	72	96	120	168	240	336	504	672	840	1176	1680	
ECG ^e	X		X						X		X	X		X	X		X	X	X		X		X		X		
Vital signs (BP, pulse rate, temperature) ^f	X		X						X		X	X	X	X	X		X	X	X	X	X	X	X	X	X	X	
Pulse Oximetry	X		X	X	X	X	X	X	X	X	X	X	X	X	X		X	X	X	X	X	X	X	X	X	X	
ADA blood sampling		X																	X		X			X		X	
CCI																											
SC Administration			X																								
SC Injection site assessment			X	X	X	X	X	X	X	X	X	X	X						X		X				X		X
PK blood sampling			X						X		X	X		X	X	X	X	X	X	X	X	X	X	X	X	X	
Urine pregnancy test ^g			X																					X		X	
Serious and non-serious Adverse Event monitoring	X	X	→	→	→	→	→	→	→	→	→	→	→	→	→	→	→	→	→	→	→	→	→	→	→	→	X
Prior/Concomitant treatments	X	X	X									X	→	→	→	→	→	→	→	→	→	→	→	→	→	→	X

Abbreviations: →= ongoing/continuous; ADA= anti-drug antibody; BP = blood pressure; ECG = electrocardiogram; HepBsAg = hepatitis B surface antigen; HepBcAb = hepatitis B core antibody; HCVA b = hepatitis C antibody; HIV = human immunodeficiency virus; IgA = immunoglobulin A; IgG = immunoglobulin G; INR = international normalized ratio; PK = pharmacokinetics; PT = prothrombin time; PTT = partial thromboplastin time; RNA = ribonucleic acid; SC = subcutaneous; TB = tuberculosis; T3 = triiodothyronine; T4 = thyroxine; TSH = thyroid stimulating hormone; TSAb = thyroid stimulating antibodies.

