6.6. Dose Progression

The participants within each cohort will be dosed using a sequential dosing scheme. For all cohorts, a single participant will be dosed at a given time, followed by a minimum of 72-hour (for IV) and 96-hours (for SC) safety monitoring period. In total there will be a minimum of 96 hours between each IV participant dosed and 120 hours for each SC participant dosed.

The following rules will be applied when considering dosing of the next participant in the cohort.

Sequential dosing may **proceed** only if no adverse events are reported OR all of the following criteria are met:

1. Any pro-inflammatory events are < Grade 2 Per CTCAE criteria in [Appendix 9](#).
2. All other adverse events are deemed mild or moderate in severity, regardless of relatedness.
3. Any laboratory, ECG or vital sign changes are considered not clinically significant.
4. No other pause or stop criteria are met.
5. For participants with ITP, in addition to the above criteria, no participant has greater than a 30% decrease in platelet count – defined from the immediate pre-dosing platelet count to the lowest postdosing platelet count. Dose progression will be independent of dose progression from HP cohorts at higher dose levels.

Sequential dosing should be **paused** if any criterion below is met in a participant receiving active drug:

1. Grade 2 (Objective) pro-inflammatory event (vomiting, diarrhea, hypotension or hypoxia) (see [Appendix 9](#)).
2. Adverse event which is considered to be severe (Grade 3 or higher) AND is deemed related to study intervention.
3. A moderate event (Grade 2) AND is deemed related to study intervention not otherwise identified as a proinflammatory event or AE of special interest, that in the opinion of the PI and Sponsor are of concern and warrant further investigation before additional dosing.
4. For participants with ITP, platelet count of <30 x 10⁹/L AND a decrease from baseline ≥30%, or a platelet count decrease from baseline of ≥50%, defined from the immediate pre-dosing platelet count to the lowest post-dosing platelet count, or a bleeding or bruising-related AE CTCAE 4.03 Grade 2 or higher (except metrorrhagia Grade 3 or higher).

Sequential dosing should be **stopped** at the current dose level if any criterion below is met in participant receiving active drug:

1. Grade 3 or greater pro-inflammatory event.
2. Serious adverse event that is deemed related to study intervention.

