10.12. Appendix 12: Country Specific Requirements

10.12.1. Czech Republic

Schedule of Activities Error! Not a valid bookmark self-reference.

Table 14. Schedule of Activities for SC Cohorts of ITP Participants- Czech Republic ONLY

Protocol Activity	Screen		Clinical Confinement																Outpatient Follow-up Visits									
			-56 to -2	-1 ^a	1											2	3	4	5	6	7	8	11 ±2	15 ±2	22 ±2	29 ±2	36 ±3	50 ±3
Study Day/Visit Window (days)			0 pre-dose	0.5	1	3	3.5	4	5	6	8	12	24	36	48	72	96	120	168	240	336	504	672	840				
Informed consent	X																											
Demography (including Height)	X																											
Outpatient Visit	X																			X	X	X	X	X	X	X	X	
Study Site Confinement		X	→	→	→	→	→	→	→	→	→	→	→	→	→	→	→	→	→	X								
Randomization			X																									
Discharge																				X								
Chest X-ray ^b	X																											
QuantiFERON-TB Gold test	X																											
HIV, HepBsAg, HepBcAb, HCVAb tests	X																											
Test for rheumatoid factor, anti-nuclear antibody, Total IgG and Total IgA, TSH, thyroxine (free T4), and triiodothyronine (free T3) TSAb; Lipid profile.	X																											
Inclusion/Exclusion	X	X																										
Medical history; history of illegal drug, alcohol & tobacco use	X	X ^c																										
Medication history	X	X ^c																										
Weight	X	X																						X			X	
Urine drug screening	X	X																										
FSH ^b	X																											
Serum Pregnancy ⁱ	X	X																		X	X	X	X	X	X	X	X	
Review contraception use	X	X																		X	X	X	X	X	X	X	X	
Physical examination ^d	X	X	X							X			X	X	X	X	X	X	X	X	X	X	X	X	X	X	X	

Protocol Activity	Screen		Clinical Confinement																	Outpatient Follow-up Visits								
	-56 to -2	-1 ^a	1											2	3	4	5	6	7	8	11 ±2	15 ±2	22 ±2	29 ±2	36 ±3	50 ±3	71 ±3 or ET	
Hour(s) Post Dose			0 pre-dose	0.5	1	3	3.5	4	5	6	8	12	24	36	48	72	96	120		168	240	336	504	672	840			
Hematology & Coagulation (PT, INR, PTT, D-dimer & fibrinogen)	X	X										X	X		X	X		X		X	X	X	X	X	X	X	X	
Safety Labs																												
Chemistry/Urinalysis/Other Safety Labs	X	X										X	X		X	X		X		X	X	X	X	X	X	X	X	
ECG ^e	X		X							X		X	X		X	X	X	X	X	X	X	X		X		X		
Vital signs (BP, pulse rate, temperature) ^f	X		X							X		X	X	X	X	X	X	X	X	X	X	X	X	X	X	X	X	
Pulse Oximetry	X		X	X	X	X	X	X	X	X	X	X	X	X	X	X	X	X	X	X	X	X	X	X	X	X	X	
ADA blood sampling		X																		X		X			X	X	X	

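### ITP cohorts: the platelet check before dosing the next participant can rest on a 72 h count, although the SC safety review runs to 96 h

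*Protocol*

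**What the plan says.** Section 4.1 requires that "A safety review of the post-dose 72-hour data (96-hour for SC administration) will occur for every participant in order to proceed". It explains the longer SC window in two steps. After IV dosing, "cytokine and laboratory abnormalities reach their peak levels within the first few hours following" Cmax. For SC dosing, where the peak had been predicted at 24 to 48 h, "preliminary data from Cohort 7 supports increasing the monitoring period to 96-hr for safety".

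Section 6.6 sets the spacing: "In total there will be a minimum of 96 hours between each IV participant dosed and 120 hours for each SC participant dosed". For ITP participants it allows dosing to proceed only if nobody has had a platelet fall above 30%, "defined from the immediate pre-dosing platelet count to the lowest postdosing platelet count". It pauses dosing if the count is below 30 x 10^9/L with a fall of at least 30%, or if the fall is at least 50%, again judged on the lowest post-dose count.

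Appendix 2 (Table 12) lists the platelet count under haematology. The haematology rows are "Hematology & Coagulation (PT, INR, PTT, D-dimer & fibrinogen) Safety Labs" in Table 3 (ITP cohorts) and "Hematology & Coagulation (PT, INR, PTT, D-dimer & fibrinogen" in Table 14 (Czech sites). Both leave the 96 h cell empty.

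Section 2.3 names the relevant risk: "High dose single IV administration of PF-06755347 may transiently lower platelet counts in healthy participants".

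**The concern.** The review was lengthened from 72 to 96 h because SC exposure peaks later than was first predicted, and the Protocol ties laboratory abnormalities to that peak. In the ITP cohorts, the one laboratory value with its own proceed and pause thresholds is the platelet count, and it is not scheduled in the added window. A fall first appearing after 72 h would be seen at 120 h, which is also the earliest time the next ITP participant may be dosed at the same level.

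These participants have little reserve. They enter at 30 to 75 x 10^9/L (Section 5.3), and all of them receive active drug. The lowest post-dose count, on which both rules depend, is only as complete as the schedule of counts behind it.

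**Working it through.** **Schedule.** I matched each mark in the haematology rows to the hours-post-dose header.

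| Source | Post-dose marks in confinement | 96 h |
|---|---|---|
| Table 3, haematology | 12, 24, 48, 72, 120, 168 h | blank |
| Table 14, haematology | 12, 24, 48, 72, 120, 168 h | blank |
| Tables 3 and 14, PK | include 72, 96 and 120 h | marked |

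Table 14 has an extra Day 7 column. Both haematology rows run through to the last visit and give the same hours, so a column shift from text extraction is unlikely. The Table 3 PK row may be displaced by one column, but 72, 96 and 120 h are filled under either alignment.

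**Gap against the rules.**
- Scheduled post-dose counts available at the 96 h review: 12, 24, 48 and 72 h, so 4 counts, of which 0 fall after 72 h.
- Part of the review window with no count: 96 - 72 = 24 h, which is all of the extension.
- Gap between scheduled counts: 120 - 72 = 48 h.
- Earliest next dose: 120 h, the same time as the next scheduled count.

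**Decisions affected.** Each ITP cohort has 3 to 6 participants dosed one at a time, which gives 3 - 1 = 2 to 6 - 1 = 5 next-participant decisions. Over two cohorts that is 4 to 10.

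**What a 30% fall means at entry counts (x 10^9/L).**
- From 30: 0.7 x 30 = 21. From 75: 0.7 x 75 = 52.5.
- Entry count below which a 30% fall takes the count under the pause level of 30: 30 / 0.7 = 42.9.

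**How likely.** Platelet reduction was seen at 1 mg/kg IV, where Cmax was 24.7 µg/mL (Section 2.3 and Table 6). The observed SC Cmax values (Table 7) are lower:
- 25 mg: 24.7 / 0.895 = 27.6-fold lower.
- 50 mg: 24.7 / 1.37 = 18.0-fold lower.
- 100 mg: 24.7 / 2.64 = 9.4-fold lower.

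Section 2.3 itself gives about 6-fold, using a predicted SC Cmax. All the observed values come from healthy participants.

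**Effect of adding a 96 h count.** The last count inside the review moves from 72 to 96 h, and the 48 h gap becomes two gaps of 24 h.

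**The case against.** The strongest reply is that the 96 h window was chosen to capture the SC Tmax and Cmax, not platelet timing. Amendment 6 added 96 h PK and cytokine/complement samples for healthy SC participants and removed other safety draws as unnecessary. Nothing in the documents shows a platelet fall beginning after 72 h, and the IV laboratory abnormalities resolved within 24 h. This lowers the likelihood. It does not remove the gap, because Section 4.1 links laboratory changes to the peak and so a later peak could move them.

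There are also safeguards. Unscheduled tests are allowed (Section 8.2.4), and a PI may extend the review (Section 4.1). A bleeding or bruising event of Grade 2 or above (Grade 3 for metrorrhagia) pauses dosing. The 96 h and 120 h limits are minimums, and a late fall blocks further dosing once it is known. These limit the harm, probably to one participant dosed before the fall is seen. The extra tests and the extension are optional, though, and none of the safeguards guarantees a platelet result between 72 h and the next dose.

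Finally, some schedule rows are blacked out, and one in Table 14 is marked at 96 h. That row is most likely cytokines and complement, given Amendment 6. A separate platelet sample cannot be wholly excluded, but the visible text places the platelet count only in the haematology panel.

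**Conclusion.** The concern holds for the ITP cohorts. As written, the platelet criterion for dosing the next ITP participant can be met on a count no later than 72 h, with 48 h between scheduled counts and none in the 24 h added to the SC review. The 4 to 10 decisions are an upper bound: the gap has effect only when the next participant is dosed before the 120 h result has been read. Later counts still feed the pause rule and the Day 8 escalation decision, so the exposure is to the next participant at the same dose and not to escalation.

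The conclusion assumes that no platelet sample sits in a blacked-out row. It does not extend to the healthy SC cohorts: Table 2, as extracted, marks haematology at 96 h. The probability of harm is likely low, but the gap is in a safety check and is cheap to close, so the change should be made.

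**What to change.** Either of two changes is enough.

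1. Add haematology, or a platelet count alone, at 96 h in Tables 3 and 14. The cost is one small extra tube at the existing 96 h PK draw, with the participant already confined to Day 8.
2. Add to Section 6.6: *For ITP cohorts, the preceding participant's 120 h platelet result must be reviewed and meet proceed criterion 5 before the next participant is dosed.* This needs no extra sample and costs a delay of hours while the result is read.

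Either needs amendment wording.
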